Exclusion criteria: (a) Diabetes mellitus or other diseases potentially associated with autonomic dysfunction [17]; (b) Treatment with antihypertensive drugs or with alpha-adrenergic antagonists; (c) Cognitive impairment, defined as a score $<$ 24 at the Montreal Cognitive Assessment (MoCA) [18]; (d) Any atypical signs lowering the diagnostic certainty for PD; (e) Lack of postural reflex defined as a score $>$ 2 at the MDS-UPDRS [13] item 3.12 [recover at the pull test]; (f) Severe levodopa induced dyskinesia, defined as a MDS-UPDRS item 4.2 $>$ 2 [functional impact of dyskinesia].

Pharmacological Therapies

Changes in medications or dosages that may affect blood pressure, other than Droxidopa, will not be allowed for the entire duration of the study (6 weeks).

Study Assessment/Procedures

Screening Visit: The PI or a member of the study team will explain the purpose, procedure, potential risks and benefits of this study, obtain the informed consent, and screen patients for Inclusion/Exclusion criteria.

Visit 1: This evaluation will be performed at least 1 hour after the first dose of dopaminergic medications, when patients are expected to be at their most optimized level of motor function. BP assessment, as per autonomic laboratory protocol, will be performed with a beat-to-beat BP monitor (Caretaker 4, Caretaker, VA, USA) and confirmed by an automated sphygmomanometer (HEM-7200 Omron Healthcare, Japan) placed at heart level on the left arm, evaluating patients in the following conditions: a) sitting in a chair

after at least 10 minutes of rest; b) after a minimum of 10 minutes of supine rest; and c) after 1 and 3 minutes of standing. These measurements will serve to (1) confirm the diagnosis of OH, and (2) evaluate for the presence of SH, defined as systolic BP \geq 150 mmHg or diastolic BP \geq 90 mmHg in the supine position [19]. Arm-cuff BP measurements will be performed with the upper arm positioned at the heart level with the feet flat on the floor. Patients will also receive training to self-monitoring BP with automated arm-cuff sphygmomanometer, which will be provided at Visit 1, and will serve to monitor BP during Droxidopa titration plan.

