WMS Assessment: Patients will be provided an Apple Watch® with dedicated app (e.g., the Activity app®), able to measure number of hours of standing per day, and total calories and active calories per day. The Apple Watch® will be connected with an iPhone and will be given to each subject together with dedicated instructions to fill out the OH-related diary. More in details, patients will be instructed to charge the Apple Watch® and the iPhone® every night before going to bed, and to wear the watch the day after when they wake up. Total number of hours in which the patients will wear the watch will be counted at the end of the study, based on the data provided by the Apple Watch®. Data collected by the Apple Watch® will be downloaded after the end of the study and will provide information related to number of steps per day, number of hours of standing per day, and total calories and active calories per day.

Droxidopa Titration Plan

Droxidopa will be started after 2 days of baseline data collection at the dosage of 100 mg 3 times a day (TID). Dose-optimization will be titrated over a 2-week period in 100- mg TID increments every 2 days until at least one of the following criteria is met:

- Self-rating score of 0 at the item 1 of the OHQ, plus an increase in standing systolic BP ≥ 10 mm Hg, compared with the baseline value, as measured 3 minutes post-standing (and 3 hours after a Droxidopa dose).
- Reaching the maximum permitted dosage of 600 mg TID.
- Sustained BP > 180 mmHg systolic or > 110 mmHg diastolic while standing, sitting, or supine.

Visit 2: Patients will receive a complete BP assessment following the same procedure detailed in Visit 1 (see above), and a standard neurological examination. Adverse events and side effects associated with Droxidopa treatment will also be addressed, adjusting the dosage of Droxidopa if needed. Technical issues related to the use of Apple Watch® will also be discussed, if present.

Visit 3: This evaluation will be performed in the morning, at 8:00 AM before breakfast and at least 1 hour after the first dose of dopaminergic medications, 4 weeks after Visit 2. Patients will undergo a complete clinical, gait, postural and BP assessment, as per the protocol described in Visit 1.

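### The sustained 180/110 mmHg limit in the droxidopa titration plan only ends dose increments: no reduction, hold or stop is attached, and it has no written effect once increments have ended

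*Combined protocol and SAP*

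**What the plan says.** The Droxidopa Titration Plan starts the drug at 100 mg TID and raises it in 100 mg TID "increments every 2 days until at least one of the following criteria is met". Three criteria follow:

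- Response: "Self-rating score of 0 at the item 1 of the OHQ, plus an increase in standing systolic BP" of at least 10 mmHg over baseline.
- Maximum dose: "Reaching the maximum permitted dosage of 600 mg TID".
- Blood pressure: "Sustained BP > 180 mmHg systolic or > 110 mmHg diastolic while standing, sitting, or supine".

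The same section says at Visit 2: "Adverse events and side effects associated with Droxidopa treatment will also be addressed, adjusting the dosage of Droxidopa if needed". A full blood pressure assessment is also done at that visit, with no action threshold stated.

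Under Study Assessment/Procedures, Visit 1, patients are trained to use an arm cuff at home, "which will be provided at Visit 1, and will serve to monitor BP during Droxidopa titration plan". The Pharmacological Therapies section states this restriction: "Changes in medications or dosages that may affect blood pressure, other than Droxidopa, will not be allowed for the entire duration of the study".

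Risks and Benefits says that the investigator explains titration and side effects before the first dose, and that a patient brochure is attached. The consent is a separate document.

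**The concern.** The first two criteria are ordinary endpoints of dose-finding: the dose works, or it can go no higher. The third is a safety event on a drug given to raise blood pressure. Listing it with the other two gives it the same single consequence, that the next increment is not taken. For a patient already above 180/110 mmHg, the question is whether the current dose should continue, and the written rule does not address that.

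The stake is patient safety. Every other medication change that may affect blood pressure is barred for the whole study, so the droxidopa dose is the one drug response to a breach that the protocol leaves open. Visit 1 also tests for supine hypertension, but no exclusion criterion or dosing rule uses the result, so patients who have it may be titrated. The protocol itself classes the study as more than minimal risk.

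**Working it through.** **What the text attaches to the limit**

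| Place | What is written | Tied to 180/110? |
|---|---|---|
| Droxidopa Titration Plan | Increments end | Yes; the only stated effect |
| Visit 1, home cuff | Training and device for use during titration; no measuring frequency, trigger value or reporting step | No |
| Clinical Diary | Postural instability, scored on three days; not blood pressure | No |
| Apple Watch data | Downloaded after the study ends | No |
| Visit 2 | Full blood pressure assessment; discretionary dose adjustment linked to adverse events and side effects | No |
| Pharmacological Therapies | Droxidopa exempt from the ban on changes | No |
| Maintenance, Visit 2 to Visit 3 | No blood pressure action rule | No |

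The limit appears once, as a condition on increments. What counts as sustained is not defined. No contact is scheduled in the supplied text between Visit 1 and Visit 2.

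**The plan's schedule, reproduced**

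From 100 to 600 mg TID there are (600 − 100) / 100 = 5 increments. At 2 days each, 600 mg TID starts 5 × 2 = 10 days after the first dose. This fits the 2-week titration period, so the schedule is consistent.

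**Day of Visit 2 (inferred)**

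Experimental Design and Patient Population gives 6 weeks of therapy, made up of 2 weeks of titration and 4 of maintenance. Visit 3 is 4 weeks after Visit 2. Visit 2 is therefore at 42 − 28 = day 14 after the first dose. The plan also says "Droxidopa will be started after 2 days of baseline data collection". If those 2 days fall inside the 2 weeks, Visit 2 is at 14 − 2 = day 12.

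**Longest wait from a breach to Visit 2**

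Formula: day of Visit 2 minus the start day of the dose step. A breach can occur at any time within a step, so the maximum is counted from the start of the step, at every dose.

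| Dose (mg TID) | Step starts (day) | Visit 2 at day 14 | Visit 2 at day 12 |
|---|---|---|---|
| 100 | 0 | 14 | 12 |
| 200 | 2 | 12 | 10 |
| 300 | 4 | 10 | 8 |
| 400 | 6 | 8 | 6 |
| 500 | 8 | 6 | 4 |
| 600 | 10 | 4 | 2 |

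**Time in which the limit has nothing left to stop**

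For a patient who reaches 600 mg TID and stays there, this runs from day 10 to day 42: 42 − 10 = 32 of 42 days. For a patient whose increments end on response before the first increase falls due on day 2, it is 42 − 2 = 40 days. With Visit 2 at day 12, Visit 3 is at 12 + 28 = day 40, and the figures are 40 − 10 = 30 and 40 − 2 = 38 days.

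**The case against.** The strongest reply is that ending increments is not an instruction to continue the dose. Droxidopa is exempt from the ban on medication changes, so it can be reduced or stopped on any day. A treating physician prescribes it, the investigator explains titration and side effects beforehand, and Visit 2 brings a full blood pressure assessment with dose adjustment available. The response criterion needs a timed standing pressure compared with baseline, which suggests that someone looks at readings between steps. Call instructions would naturally sit in the brochure, the consent document or the contact pages, none of which can be seen here.

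Most of this stands, and it rules out two stronger readings:

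- A reader might infer that a patient in breach must stay on the same dose until Visit 2. The text does not say so; silence is not an order to continue.
- A reader might infer that a home reading has no way of reaching the team before Visit 2. The documents cannot support that, because the material most likely to describe such a route is not in the supplied text.

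What the reply does not do is tie an action to the limit. Permission to change the dose is not a rule for when to change it. The Visit 2 adjustment is discretionary and does not refer to 180/110 mmHg. Competent clinicians would probably act, but a stated safety limit should not depend on that inference.

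**Conclusion.** The point holds as a gap in the written safety rule. Ending increments is the limit's only stated consequence, and after increments have ended it has none. This is more than missing detail, because the rule as written handles a safety breach on a vasopressor as an ordinary titration endpoint.

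The size can be given only as calendar maxima. The wait to Visit 2 is at most 14 days at 100 mg TID, falling to 4 days at 600 mg TID (12 falling to 2 under the alternative calendar). For a patient who reaches and stays at 600 mg TID, the limit has no written effect for about three quarters of treatment (32/42 = 76%). These figures rest on an inferred Visit 2 day and are not expected delays. The documents give no breach rate, so no expected number of affected patients among the 12 can be stated.

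The change should be made, with medium confidence: the brochure or consent may already contain the missing instruction, in which case a cross-reference closes much of the gap.

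**What to change.** Take the limit out of the dose-optimisation list and make it a separate safety criterion. Suggested text:

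> If home blood pressure is above 180 mmHg systolic or 110 mmHg diastolic in any position, the patient rests and repeats the reading. If the repeat is still above the limit, the patient takes no further increment and calls the study team the same day. The study physician, with the prescribing physician, reduces or holds droxidopa unless a reason to keep the dose is recorded.

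The amendment should also:

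- state the interval before the repeat reading (a clinical choice; the documents give no figure), so that sustained has a working definition;
- name who acts as study physician, since the protocol does not use that title;
- apply the criterion during titration, when home-cuff monitoring is already planned, and to the clinic blood pressure at Visit 2 before maintenance begins;
- for maintenance, ask patients to keep using the cuff already supplied and to call on the same limit, because home monitoring is at present written only for titration.

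If the brochure or consent already says this, cite it in the Droxidopa Titration Plan.

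Cost: a short protocol amendment, an added line in the home-cuff instructions and a field in the contact log. There will be some unscheduled calls, including during maintenance, and a few patients may be on a lower dose at Visit 3. Endpoints and the sample size of 12 are unchanged.

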Title of the Study: Technology-Based Objective Measures for Gait and Postural Assessment in Parkinson Disease Patients with Orthostatic Hypotension: Feasibility and Effect-Size Finding Study.

Principal Investigator: [name], MSc

Funding: Investigator-initiated study sponsored by Lundbeck

BACKGROUND:

Neurogenic orthostatic hypotension (OH) is a frequent and disabling complication of Parkinson's disease (PD), with an estimated prevalence of 30-50% [1-3], and a significant impact on the quality of life (QoL). OH may be associated with potentially serious complications, such as postural instability, gait impairment, and falls, which directly or indirectly (e.g., fractures) represent the most frequent cause of hospitalization in PD [4-6].

The lack of objective measures for the assessment of OH disability, however, represents a clinical challenge in the management of this complex hemodynamic condition. Although different scales have been developed for the assessment of orthostatic intolerance in PD [7], their application is limited by the substantial proportion of patients not reporting "classic" OH symptoms, namely dizziness, lightheadedness, or "feeling like you might black out while standing" [7]. Up to 50% of OH patients may complain symptoms such as weakness, vertigo, and difficulty concentrating, which may be erroneously diagnosed, underestimated, and thus undertreated. In a recent study, we demonstrated that OH might cause a 3-fold risk of gait impairment and functional disability in PD, regardless of the presence/absence of postural lightheadedness [8].

Clinical assessment and monitoring of OH symptoms relies on inaccurate and highly subjective clinical measures based on quantification of symptoms that are frequently ambiguous and not specific. In a recent study where we assessed the impact of autonomic dysfunction in 121 consecutive PD patients, OH was independently associated with gait impairment and functional disability, regardless of the symptomatic or asymptomatic status [8]. These data support the hypothesis that clinical scales currently available for quantifying the severity of OH are not adequate for capturing the full complexity of this frequent yet under-recognized PD complication.

Technology-Based Objective Measures (TOMs)

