The introduction of TOMs in medical care represents one of the most promising aspects of modern medicine [14]. TOMs may quantify the severity of PD motor symptoms and increase the diagnostic accuracy of different challenging conditions. In addition, the growing access to high-speed internet connection may facilitate continuous communication and remote assessment of data collected via TOMs during normal activities of daily living, providing accurate monitoring of patients in their home environment. Possible advantages will include the reduction of placebo effect due to in-clinic evaluations, higher sensitivity in the accuracy of outcome measures, and a substantial decrease in sample size and duration of clinical trials.

Future Directions

Currently, TOMs application in clinical trials is limited by the lack of validation studies proving the feasibility and reproducibility of measuring therapeutic outcomes via technological sensors. Preliminary data collected in this study will prove the feasibility of using TOMs for assessing the effects of anti-OH

treatment, informing the design of a major proposal aiming to evaluating the beneficial effects of an early treatment for the prevention of OH complications in PD.

Experimental Design and Patient Population

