Data will be described with appropriate summary measures (mean and SD, or median and interquartile range) at Visit 1 (before Droxidopa treatment) and Visit 3 (after 4 weeks of Droxidopa maintenance therapy). Changes in the main clinical (PDQ-39, Tinetti, OHQ and related subscales), gait (stride length, single leg stance time, dynamic stability index, and gait velocity) and postural (postural sway on the X and Y axis) outcomes will be compared between Visit 1 and Visit 3 using the paired t-test/ non parametric Wilcoxon signed rank test depending on the distribution of change outcome. Effect size (mean or median change and percent change) will be reported along with 95% confidence interval (CI). In addition, data collected with TOMs before and after treatment with Droxidopa will be correlated with changes in the PDQ-39, OHQ, CANTAB and CERAD-NAB by means of the Pearson correlation/Spearman rank correlation analysis.

Hypothesis: Gait analysis and Postural analysis will accurately capture changes in gait and postural stability associated with OH treatment, with higher sensitivity and lower variability than standard clinical tests.

Aim #2 To evaluate the feasibility and calculate the effect size of using WMS to quantify OH related functional parameters during at-home activities of daily living

Postural data collected from WMS (Apple Watch®) and evaluating: (1) Number of steps per day; (2) number of hours of standing per day; and (3) total calories and active calories per day, will be analyzed and compared with episodes of subjective (OHDAS-based diary) postural instability recorded during the follow-up period using a paired t-test/Wilcoxon signed rank test. In addition, we would also evaluate the changes from pre-baseline to post baseline of subjective measure of postural stability and correlate with objective measures of postural stability using Pearson correlation/Spearman rank correlation analysis. Statistical analyses will be carried out using SAS 9.3.

Hypothesis: WMS will provide an accurate measure of functional parameters in the home setting, thus allowing an indirect measure of the patients' quality of life, with higher sensitivity and lower variability than self-reported clinical diaries.

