Missing data on the scores will be handled by a two-step approach. Less than 20% missing data on any variable for an individual will be imputed using the mean of the final score of that question. Greater than 20% missing data for any participant on any instrument will be handled by a multiple missing imputation approach. Missing data on BP related variables will be imputed using multiple missing imputation approach.

Sample Size Calculation: Given the exploratory nature of this pilot study, the sample size calculation is inevitably limited by the lack of previous data. We used a study analyzing the effect of levodopa in PD with

a gait analysis [21], which reported a 30% improvement in the stride length (SD 31.3%), to pre-specify a threshold of minimal improvement of 10% between baseline and follow-up. With these assumptions, we estimate that a sample of 12 patients will be more than sufficient to detect significant differences using a paired t-test, with more than 80% power and at 5% level of significance (PASS 14 Power Analysis and Sample Size Software (2015). NCSS, LLC. Kaysville, Utah, USA, ncss.com/software/pass).

Innovation

Although TOMs are unanimously thought to represent the future of medical assessments, their routine application is limited by the lack of validation studies proving their efficacy and reliability in clinical trials. The current proposal will provide more sensitive standards for the assessment of OH complications in PD, with the main innovation of developing and validating an innovative outcome measure based on a mobile (WMS) and in-clinic (gait analysis) technology.

DATA STORAGE AND CONFIDENTIALITY:

All records from this study will be maintained in a secure setting. We will be using REDCap (Research Electronic Data Capture) as the secure web-based application to store data for this research study. Records will not have any patient health information (PHI) associated with them. These records will be kept indefinitely to allow for re-analysis of data, if needed. The data will never be accessible without a secure password.

RISKS AND BENEFITS:

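### Aim 1 lets the 12 observed changes choose the test and gives no rule for mean versus median change, so with skewed changes the reported effect size has no fixed target

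*Combined protocol and SAP*

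**What the plan says.** In the combined protocol and SAP, Data Analysis, Aim #1, the changes in the clinical, gait and postural outcomes from Visit 1 to Visit 3 are compared "using the paired t-test/ non parametric Wilcoxon signed rank test depending on the distribution of change outcome". The next sentence reads "Effect size (mean or median change and percent change) will be reported along with 95% confidence interval (CI". The summaries at the two visits are equally open: "Data will be described with appropriate summary measures (mean and SD, or median and interquartile range".

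No section gives a criterion for judging the distribution, a rule for choosing mean or median, or a CI method for a median. The Sample Size Calculation says earlier data are lacking, so the shape can only be judged from the study's own 12 patients.

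The effect size is a named product of the study. The title calls it a "Feasibility and Effect-Size Finding Study", both aims repeat this, and Future Directions gives its use as "informing the design of a major proposal". The Aim 1 hypothesis compares gait and postural measures with clinical scales, "with higher sensitivity and lower variability than standard clinical tests".

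**The concern.** A planning value should estimate one quantity fixed beforehand. Here the sample that supplies the estimate also appears to decide what is estimated. Three consequences follow.

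- For skewed changes, the reported figure is a mean in some samples and a median in others. Over repeated samples it has no single target.
- Within one study, some outcomes may carry means and others medians. The sensitivity and variability of sensors and clinical scales then cannot be set side by side on a common measure.
- A larger study planned on a paired t-test, as this one was, needs the mean change and the SD of change. The plan promises SDs (or interquartile ranges) at each visit, not of the change. If a mean with a t-interval is reported, the SD of change can be recovered as half-width × √12 / 2.201. From a median and its interval it cannot.

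There is also a secondary point. The signed-rank test does not test the sample median; its matching estimate is the Hodges-Lehmann pseudo-median. A median with an order-statistic interval can therefore disagree with the Wilcoxon p-value printed beside it.

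**Working it through.** **Inputs from the document.** n = 12 paired changes; 5% significance level; source effect 30% with SD 31.3%; threshold 10% (Sample Size Calculation).

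**Assumptions, because the plan gives none.** The switch to Wilcoxon and median occurs when Shapiro-Wilk p < 0.05. The mean has a t-interval. The median has the interval from the 3rd to the 10th ordered value, with exact coverage 1 − 2 × (1 + 12 + 66)/4096 = 0.961. The signed-rank test is exact, rejecting at W ≤ 13 (true size 4.2%). The shapes of the changes are assumed.

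**The plan's own figure.** The plan gives no figure on this choice. Its only related figure is the sample size, "a sample of 12 patients will be more than sufficient to detect significant differences using a paired t-test". Taking 31.3% as the SD of change, 30/31.3 = 0.96 gives two-sided power of 85.5%. The stated 10% threshold gives 17.3%. That mismatch is a separate matter, and nothing below depends on it.

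**Check 1: what the rule estimates (unit SD).** Exponential changes shifted to mean 0.80 have median 0.80 − (1 − ln 2) = 0.49. Over 12,000 samples, 54% switch and the reported effect averages 0.60. For normal changes about 5% switch and there is no bias.

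**Check 2: the same on the percent scale.** SD of change 31.3, true mean 10, 20,000 samples per shape:

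| Shape | True median | Mean reported in | Average reported effect | Coverage of mean, switching rule | Coverage of mean, t-interval always |
|---|---|---|---|---|---|
| Normal | 10.0 | 95% | 10.0 | 0.947 | 0.950 |
| Lognormal, sigma 0.5 | 3.1 | 70% | 6.7 | 0.895 | 0.924 |
| Lognormal, sigma 0.8 | 0.95 | 44% | 3.7 | 0.818 | 0.883 |
| Exponential | 0.4 | 46% | 3.75 | 0.862 | 0.910 |

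The exponential row shows the mechanism. The average is 10.01 when the mean is reported and −1.51 when the median is: 0.456 × 10.01 + 0.544 × (−1.51) = 3.74, which agrees with 3.75 up to rounding. Judged against the median, the switching rule covers 0.915-0.933 in the three skewed rows, and a median interval used throughout covers about 0.96.

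**Check 3: type I error.** With true mean 0, the switching rule rejects in 5.0% (normal), 10.1% (exponential) and 13.0% (lognormal 0.8) of samples. The t-test alone rejects in 4.9%, 9.6% and 11.7%. Switching adds at most 13.0 − 11.7 = 1.3 points; the rest comes from skew at n = 12.

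**Check 4: interval against test.** Take changes −4, −3, −2, 1, 5, 6, 7, 8, 9, 10, 60, 75.

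- Shapiro-Wilk p = 0.0003, so the rule switches.
- The negative values hold ranks 4, 3 and 2, so W = 9 and Wilcoxon p = 0.016.
- The median is (6 + 7)/2 = 6.5, with interval −2 to 10, which includes 0.
- The Hodges-Lehmann interval is 1.5 to 35, which agrees with the test.
- The mean is 172/12 = 14.3, with t-test p = 0.077.

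At mean 0.8 and SD 1, a significant Wilcoxon result with a median interval that includes 0 occurs in about 0.7% (normal), 4% (lognormal 0.8), 6% (gamma with shape 2) and 15% (exponential) of all samples.

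**The case against.** The strongest objection is that the switch in effect measure is inferred. Only the test is tied to the distribution of the changes; the effect-size sentence has no selection rule, and reporting both measures for every outcome would not breach it. A Hodges-Lehmann interval is also compatible with the text. This stands, so the pairing must be presented as a reading. It does not remove the point: on any other reading, the choice of measure is even less constrained.

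Second, no document gives the shape of the changes. If they are symmetric, mean and median share a target and nothing is biased. This stands.

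Third, sampling error is larger than the effect shown. The 95% half-width is 2.201 × 31.3/√12 = 19.9 percentage points, against a mean-median gap of 10 − 3.1 = 6.9 to 10 − 0.4 = 9.6 points in the skewed rows. This also stands, but the interval tells the reader about sampling error and not about a change of target.

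Fourth, records are kept indefinitely for re-analysis, so the mean and SD of change could be computed later. That is true: the data are not lost, only the promised report is incomplete.

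Fifth, the mean is not the only defensible choice, particularly for bounded scales, and its t-interval under-covers with strong skew. This is fair, and it is why a fixed robustness column belongs in the fix.

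Four stronger readings are tempting and not supported.

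- A reader might infer that the rule inflates false positives; Check 3 shows that switching adds little.
- A reader might infer that test and interval usually conflict. They conflict in a minority of samples, and only if an order-statistic interval is used. Among switched samples with a significant Wilcoxon result, the rate was 7% for lognormal 0.8 and 34% for exponential changes, so no general rate can be quoted.
- A reader might put a probability on outcomes carrying mixed measures. That needs independent outcomes, which the OHQ and its own subscales are not; and for normal changes an accidental switch causes no bias.
- A reader might infer that the Wilcoxon route clashes with the missing-data paragraph, where larger gaps "will be handled by a multiple missing imputation approach". That applies to more than 20% missing on an instrument and to blood pressure, which is not in the Aim 1 outcome list. A mean change pools more directly, but this is a side benefit.

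**Conclusion.** The point holds as a cheap improvement that should be made. The observed changes choose the test, the plan states no rule for mean or median, and it does not promise the SD of change, although effect size is a named product of the study.

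The size depends on skew. It is nil for symmetric changes. For exponential changes with mean 0.80 and median 0.49, 54% of samples switch and the reported effect averages 0.60. On the percent scale with true mean 10, the reported effect averages 3.7 to 6.7 in the skewed shapes. These figures rest on the inferred pairing of measure with test, the assumed Shapiro-Wilk switch and the assumed shapes. The disagreement between median interval and Wilcoxon test is secondary.

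Because this is an exploratory pilot, the consequence is planning values that are mis-targeted or not comparable across outcomes. The documents do not support reading it as a false confirmatory claim.

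**What to change.** In Data Analysis, Aim #1:

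- Delete the clause that makes the test depend on the shape of the changes.
- For every outcome, fix the estimate in advance as mean change, SD of change and the 95% CI from the paired t-test.
- Beside it, for every outcome, give the signed-rank test with the Hodges-Lehmann estimate and its matching CI, labelled as a robustness analysis. This replaces the sample median.

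The cost is SAP wording and one extra output column, with no change to visits, data collection or sample size. The downside is that the t-interval covers the mean at roughly 88-93% under strong skew. A clear gap between the two columns would warn the reader of skew.
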